5.3.1 Acceptable Concomitant Medications

All treatments that the Investigator considers necessary for a subject's welfare may be administered at the discretion of the Investigator in keeping with the community standards of medical care. All concomitant medication will be recorded on the case report form (CRF), including all prescription, over-the-counter (OTC), herbal supplements, and IV medications and fluids. If changes occur during the trial period, documentation of drug, dosage, frequency, route, and date should also be included on the CRF.

All concomitant medications received within 28 days before the first dose of trial treatment and 30 days after the last dose of trial treatment should be recorded. Concomitant medications administered after 30 days after the last dose of trial treatment should be recorded for SAEs and ECIs as defined in Section 9.0.

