^hQuestionnaires: AUA IPSS and QOL will be completed prior to any treatment or procedures scheduled for that visit.* To monitor for systemic dissemination of BCG infection, daily phone calls of days 2-4 of each cycle of BCG treatment (Weeks 7-12) will occur to monitor for fever and symptoms of systemic infection. Subjects will each be given an oral thermometer and a diary to record oral temperature twice daily (morning and evening) and to record any symptoms they may be having. The diary will be utilized Days 1-7 for each of the 6 BCG cycles (Weeks 7-12).

ⁱTrans-urethral Resections: All TURB will occur as part of SOC and as clinically indicated. Screening cystoscopy/TURBT window is 90 days prior to the start of treatment.

^jAdverse Events will be collected from time of main study informed consent through 30 days post last study drug infusion/treatment.

^kPhysical Exam: Full physical exams are required at screening and at the 30 day follow up. All other exams may be symptom directed.

^lPerformance status: ECOG performance status scale should be used to measure performance status.

^mECG, Chest X-ray, and Pulmonary Function Tests will be completed prior to Day 1 Cycle 1 and will only be repeated as clinically indicated.

ⁿPT/INR and aPTT will be completed prior to all resections/ possibly biopsies as standard of care. All other monitoring of PT/INR and aPTT will only be completed as clinically indicated (i.e. if on Coumadin).

^oCystoscopy will be performed as standard of care, but will be considered measures for efficacy. Biopsy will be performed as clinically indicated.

Product: MK-3475

Protocol/Amendment No.: Amendment 5, 21 October 2019

^pSpecimen Collection/Correlative studies: Whole blood, serum, and urine will be collected at time of consent or may be collected at any time prior to treatment on Day 1 of Cycle 1. Specimens for correlative study will also occur at each visit through Week 19, repeat cystoscopy (12 visits). Saliva will be collected only at baseline. Tumor tissue will only be collected at Week 19 biopsy, if a biopsy is clinically indicated at the time of cystoscopy. Specimen collection is requested at the 3, 6, 9, 12, 18, and 24 month follow up visits if subject is being treated locally at the site, though not required. Tissue will only be collected if a biopsy is clinically indicated at time of cystoscopy.

^qChest X-rays performed in the 90 days window prior to the screening visit are acceptable.

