8.1.2.2 Adverse Event (AE) Monitoring

The Investigator or qualified designee will assess each subject to evaluate for potential new or worsening AEs as specified in the Trial Flow Chart and more frequently, if clinically indicated. Adverse experiences will be graded and recorded throughout the study and during the follow-up period according to NCI CTCAE Version 4.0 (Appendix E). Toxicities will be characterized in terms regarding seriousness, causality, toxicity grading, and action taken with regard to trial treatment. AEs will be recorded from the time the subject signs the consent through 30 days post the last study treatment.

Please refer to section 9.0 for detailed information regarding the assessment and recording of AEs.

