8.1.6.5 Treatment Discontinuation/Safety Follow-Up Visit

The Treatment Discontinuation Visit and Safety Follow-Up Visit include identical procedures and assessments. Subjects withdrawn from treatment prior to completion of the Treatment Period should undergo a Discontinuation Visit for safety purposes and may occur any time within 30 days of the subject discontinuing treatment, but preferably prior to the subject initiating a new treatment. The mandatory Safety Follow-Up Visit should be conducted approximately 30 days after the last dose of trial treatment or before the initiation of a new anti-cancer treatment, whichever comes first. All AEs that occur prior to the Safety Follow-Up Visit should be recorded. Subjects with an AE of Grade >1 will be followed until the resolution of the AE to Grade 0-1 or until the beginning of a new anti-neoplastic therapy,

Product: MK-3475

Protocol/Amendment No.: Amendment 5, 21 October 2019

whichever occurs first. SAEs that occur within 30 days of the end of treatment or before initiation of a new anti-cancer treatment should also be followed and recorded.

Assessments at the Discontinuation/Safety Follow-Up Visit include a full physical examination, ECOG Performance Status and vital signs. Laboratory assessments include hematology, chemistry, and urinalysis, as well as evaluation of thyroid function. Concomitant medications and toxicity assessment will be recorded as well.

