9.0 ASSESSING AND RECORDING ADVERSE EVENTS

An adverse event is defined as any untoward medical occurrence in a patient or clinical investigation subject administered a pharmaceutical product and which does not necessarily have to have a causal relationship with this treatment. An adverse event can therefore be any unfavorable and unintended sign (including an abnormal laboratory finding, for example), symptom, or disease temporally associated with the use of a medicinal product or protocol-specified procedure, whether or not considered related to the medicinal product or protocol-specified procedure. Any worsening (i.e., any clinically significant adverse change in frequency and/or intensity) of a preexisting condition that is temporally associated with the use of the investigational product, is also an adverse event.

Changes resulting from normal growth and development that do not vary significantly in frequency or severity from expected levels are not to be considered adverse events. Examples of this may include, but are not limited to, teething, typical crying in infants and children and onset of menses or menopause occurring at a physiologically appropriate time.

Adverse events may occur during the course of the use of investigational product in clinical trials, or as prescribed in clinical practice, from overdose (whether accidental or intentional), from abuse and from withdrawal.

Progression of the cancer under study is not considered an adverse event.

All adverse events that occur after the consent form is signed, but before treatment allocation/randomization, must be reported by the Investigator if they cause the subject to be excluded from the trial, or are the result of a protocol-specified intervention, including, but

Product: MK-3475

Protocol/Amendment No.: Amendment 5, 21 October 2019

not limited to, washout or discontinuation of usual therapy, diet, placebo treatment or a procedure.

From the time of treatment allocation/randomization through 30 days following cessation of treatment, all adverse events must be reported by the Investigator. Such events will be recorded at each examination on the Adverse Event case report forms/worksheets. The reporting timeframe for adverse events meeting any serious criteria is described in section 9.1.3.1.

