9.1.3 Immediate Reporting of Adverse Events to the Sponsor

9.1.3.1 Serious Adverse Events

A serious adverse event is any adverse event occurring while the subject is enrolled into the study that:

- Results in death;
- Is life threatening;
- Results in persistent or significant disability/incapacity;
- Results in or prolongs an existing inpatient hospitalization;
- Is a congenital anomaly/birth defect;
- Is another important medical event

Note: In addition to the above criteria, adverse events meeting either of the below criteria, although not serious per ICH definition, are reportable to the Merck in the same timeframe as SAEs to meet certain local requirements. Therefore, these events are considered serious by Merck for collection purposes.

- Is a new cancer (that is not a condition of the study);
- Is associated with an overdose.

Product: MK-3475

Protocol/Amendment No.: Amendment 5, 21 October 2019

Refer to Table 8 for additional details regarding each of the above criteria.

Progression of the cancer under study is not considered an adverse event unless it results in hospitalization or death.

For the time period beginning when the consent form is signed until treatment allocation/randomization, any serious adverse event, or follow up to a serious adverse event, including death due to any cause other than progression of the cancer under study, that occurs to any subject must be reported within 24 hours to the Sponsor and within 2 working days to Merck Global Safety if it causes the subject to be excluded from the trial, or is the result of a protocol-specified intervention, including, but not limited to, washout or discontinuation of usual therapy, diet, placebo treatment or a procedure.

For the time period beginning at treatment allocation/randomization through 90 days following cessation of treatment, or 30 days following cessation of treatment if the subject initiates new anticancer therapy, whichever is earlier, any serious adverse event, or follow up to a serious adverse event, including death due to any cause other than progression of the cancer under study, whether or not related to the investigational product, must be reported within 24 hours to the Sponsor (and Merck Global Safety if a Merck product.)

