9.1.3.2 Events of Clinical Interest

Selected non-serious and serious adverse events are also known as Events of Clinical Interest (ECI) and must be reported within 24 hours to the Sponsor and within 2 working days to the product manufacturer safety division.

For the time period beginning when the consent form is signed until treatment allocation/randomization, any ECI, or follow up to an ECI, that occurs to any subject must be reported within 24 hours to the Sponsor and within 2 working days to Merck Global Safety if it causes the subject to be excluded from the trial, or is the result of a protocol-specified

Product: MK-3475

Protocol/Amendment No.: Amendment 5, 21 October 2019

intervention, including, but not limited to, washout or discontinuation of usual therapy, diet, placebo treatment or a procedure.

For the time period beginning at treatment allocation/randomization through 90 days following cessation of treatment, or 30 days following cessation of treatment if the subject initiates new anticancer therapy, whichever is earlier, any ECI, or follow up to an ECI, whether or not related to Merck product, must be reported within 24 hours to the Sponsor and within 24 hours to Merck Global Safety.

Events of clinical interest for this trial include:

1. An overdose of study drug, as defined in Section 9.1.1 - Definition of an Overdose for this Protocol and Reporting of Overdose to the Sponsor, that is not associated with clinical symptoms or abnormal laboratory results.
2. An elevated AST or ALT laboratory value that is greater than or equal to 3X the upper limit of normal and an elevated total bilirubin laboratory value that is greater than or equal to 2X the upper limit of normal and, at the same time, an alkaline phosphatase laboratory value that is less than 2X the upper limit of normal, as determined by way of protocol-specified laboratory testing or unscheduled laboratory testing.*

***Note:** These criteria are based upon available regulatory guidance documents. The purpose of the criteria is to specify a threshold of abnormal hepatic tests that may require an additional evaluation for an underlying etiology.

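### SAE windows conflict (30 v 90 days), and 10.1 has no onset or end rule, so the primary safety table can include pre-dose events and miss SAEs from days 31-90

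*Combined protocol and SAP*

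**What the plan says.** **End of the window.** For SAEs, section 9.1.3.1 covers the period "beginning at treatment allocation/randomization through 90 days following cessation of treatment", cut to 30 days if new anticancer therapy starts. Section 9.1.3.2 gives ECIs the same limit: "through 90 days following cessation of treatment, or 30 days following cessation of treatment if the subject initiates new anticancer therapy". The end of 9.1.3.1 adds that an SAE judged related is reportable whenever the investigator learns of it. Section 9.0 defers to this: "The reporting timeframe for adverse events meeting any serious criteria is described in section 9.1.3.1". Section 5.3.1 fits the longer window, since concomitant medications given "after 30 days after the last dose of trial treatment should be recorded for SAEs and ECIs as defined in Section 9.0".

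Three other places use 30 days. Footnote j of the flow chart says that adverse events "will be collected from time of main study informed consent through 30 days post last study drug infusion/treatment". Section 8.1.2.2 says "AEs will be recorded from the time the subject signs the consent through 30 days post the last study treatment". Neither excepts serious events. Section 8.1.6.5 asks sites to follow and record "SAEs that occur within 30 days of the end of treatment or before initiation of a new anti-cancer treatment".

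**Start of the window.** Footnote j and 8.1.2.2 start at consent. Section 9.0 starts the general duty later: "From the time of treatment allocation/randomization through 30 days following cessation of treatment, all adverse events must be reported by the Investigator". Before that point it asks only for events that lead to exclusion or result from a protocol-specified intervention.

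**Follow-up and analysis.** Section 8.1.6.6 lists disease status, new therapy, recurrence, progression, death and end of study as the follow-up content. For the primary objective, section 10.1 gives one sentence on AEs: the proportion of patients with each AE, with its CTCAE grade. The only population named is the intent-to-treat population of screened and enrolled subjects in 5.7.

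**The concern.** The AE table is the main product of a trial whose primary objective is safety. Two analysts following this document could build different tables. One could count everything collected from consent to day 30. The other could start at the first dose and carry SAEs to day 90.

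The start matters because subjects may consent before the restaging resection (5.1.1), and screening includes cystoscopy (8.1.6.1.1). Bleeding or urinary symptoms after those procedures could resemble the dysuria and hematuria that 5.2.1.4 lists as common with BCG. Without an onset rule they can fall in the same row.

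The end matters because 5.2.3.3 itself warns that drug-related events may appear several months after the last dose. If no one asks about days 31-90, the table depends on what happens to reach the investigator.

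**Working it through.** **1. The windows side by side**

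| Place | Events | Start | End |
|---|---|---|---|
| Footnote j; 8.1.2.2 | AEs, SAEs not excepted | Consent | 30 days |
| 9.0 | All AEs; SAE timing sent to 9.1.3.1 | Allocation/randomization | 30 days |
| 9.1.3.1; 9.1.3.2 | SAEs; ECIs | Allocation/randomization | 90 days, or 30 with new therapy |
| 9.1.3.1, later paragraph | Related SAEs | Not limited | None |
| 8.1.6.5 | SAEs | Not stated | 30 days, or start of new therapy |
| 10.1 | Each AE | Not stated | Not stated |

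For non-serious AEs other than ECIs, the 30-day end is consistent throughout. The conflict concerns SAEs and ECIs.

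**2. Reading 8.1.6.5.** That section's other two time limits (visit timing and AE follow-up) say that the earlier date governs. The SAE limit does not, so two readings are open.
- *The earlier date governs.* Recording stops at day 30 at the latest, which conflicts with 9.1.3.1 for every subject without new therapy.
- *Either condition is enough.* An SAE after day 30 is recorded as long as no new therapy has started. But for a subject who starts therapy between days 31 and 90, this runs to the start of therapy, while 9.1.3.1 ends at day 30.

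Neither reading reproduces the 9.1.3.1 window.

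**3. The start point.** The trial summary describes a non-randomized trial with a single treatment group, so allocation/randomization is not a defined event. It could mean registration (8.1.1.7) or first dose.

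**4. Does an existing contact reach day 90?** Taking 3 months as 91 days:
- Last scheduled MK-3475 dose, Week 16 Day 1: 15 × 7 + 1 = day 106. Adding 30 gives day 136; adding 90 gives day 196.
- 3-month contact counted from completion of treatment (8.1.6.6): 106 + 91 = day 197, one day past the window.
- 3-month contact counted from the Week 19 cystoscopy (footnote d): 18 × 7 + 1 = day 127; 127 + 91 = day 218; 218 − 106 = 112 days after the last dose, 22 days past the window.

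The contact nominally falls after day 90 on either count. On the first count the margin is one day, and footnote d calls the visits approximate and open to shifts. A contact that falls early would leave part of the window uncovered.

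**5. Scale.** One of 15 subjects is 1/15 = 6.7 points. Exact 95% intervals are 0 to 21.8% for 0/15 and 0.2 to 31.9% for 1/15.

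The documents give no late-SAE rate. For illustration only, let p be an **assumed** per-subject probability of an SAE in days 31-90, with no one starting new therapy by day 90. The chance of at least one such subject among 15 is 1 − (1 − p)^15, and the expected number is 15p:

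| Assumed p | Chance of at least one | Expected subjects |
|---|---|---|
| 1% | 1 − 0.860 = 14.0% | 0.15 |
| 5% | 1 − 0.463 = 53.7% | 0.75 |
| 10% | 1 − 0.206 = 79.4% | 1.5 |

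At each assumed rate these are upper limits on what the table could miss, because such SAEs must be reported once known.

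**The case against.** The strongest reply is that the reporting duty is already sound. Section 9.0 names 9.1.3.1 as the authority for SAE timing. Known SAEs to day 90 must be reported within 24 hours whether or not they are related, and related SAEs have no time limit. Unplanned visits record toxicity (8.1.6.3), deaths are collected at follow-up, and 10.1 contains no cut-off that would drop a late SAE. A reader might infer from the 30-day statements that late SAEs are lost to the sponsor. The documents do not support that.

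Nor do they support the reading that 8.1.6.5 plainly stops at 30 days and is the only place out of line. Its wording can be read past day 30, and footnote j and 8.1.2.2 carry a 30-day end that also covers SAEs.

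Other points carry some weight. Recording from consent can coexist with a narrower duty to report, and baseline effects are documented at screening. The analysis is descriptive. The Week 19 cystoscopy falls 127 − 106 = 21 days after the last dose, so subjects found to have recurrence may start new therapy, and their window is then 30 days. Appendix F describes post-treatment samples as already collected, so for some subjects only a retrospective check may remain.

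Two gaps survive all of this. No listed follow-up item looks for SAEs in days 31-90, and 10.1 does not say which events count. A duty to report known events does not find unknown ones or settle what enters the table.

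**Conclusion.** The point holds as a gap in ascertainment and in table definition, and should be fixed. Followed as written, the plan can put pre-dose events into the primary safety table and can leave out SAEs from days 31-90.

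The size cannot be stated. It depends on a late-event rate that the documents do not give and on how many subjects start new therapy, since their window closes at 30 days. The firm figure is 6.7 points for each subject classified differently, at 15 subjects.

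A reader might also infer that dose escalation is compromised. It is not: that rule turns on doses withheld or discontinued for toxicity, not on this table. The stopping rules for fatal and grade 4 events (5.8) state no such window either.

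**What to change.** 1. Reconcile 8.1.6.5, footnote j and 8.1.2.2 with the 9.1.3.1/9.1.3.2 window for SAEs and ECIs, and keep 30 days for other AEs. Changing 8.1.6.5 alone would leave two 30-day statements standing.
2. Add one SAE/ECI question to the existing 3-month contact or chart review, covering days 31-90 in full. If that contact falls before day 90, complete the remaining days by chart review or at the next existing contact. For subjects already past it, use retrospective chart review, which footnote d already allows as a source. No new visit is needed.
3. Replace allocation/randomization with an event defined in this trial, such as first dose.
4. State in 10.1 that:
   - the primary safety table covers subjects who received at least one dose, and counts AEs that start or worsen from first dose to 30 days after last dose;
   - SAEs and ECIs to the 90-day limit (30 if new therapy starts) appear in a separate row or table;
   - pre-dose events and later related SAEs are listed separately.

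The start dates (Table 8) and grade changes (9.1.4) needed for these rules are already recorded. The cost is amendment wording, a little extra data entry and possibly a higher reported SAE proportion. Retrospective review may still miss events treated elsewhere.

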8.1.6.6 Follow-up Visits

Subjects who complete all study treatment or discontinue trial treatment for a reason other than disease progression will move into the Follow-Up Phase and should be assessed at 19 week cystoscopy. Additional follow up information will be collected at 3, 6, 9, 12, 18, and 24 months post completion of treatment. Every effort should be made to collect information regarding disease status, start of new anti-neoplastic therapy, disease recurrence, disease progression, death, or end of the study. Information regarding post-study anti-neoplastic treatment will be collected if new treatment is initiated.

A final set of AUA IPSS and QOL questionnaires are also to be administered at the 3 month Follow Up visit.

9.0 ASSESSING AND RECORDING ADVERSE EVENTS

An adverse event is defined as any untoward medical occurrence in a patient or clinical investigation subject administered a pharmaceutical product and which does not necessarily have to have a causal relationship with this treatment. An adverse event can therefore be any unfavorable and unintended sign (including an abnormal laboratory finding, for example), symptom, or disease temporally associated with the use of a medicinal product or protocol-specified procedure, whether or not considered related to the medicinal product or protocol-specified procedure. Any worsening (i.e., any clinically significant adverse change in frequency and/or intensity) of a preexisting condition that is temporally associated with the use of the investigational product, is also an adverse event.

Changes resulting from normal growth and development that do not vary significantly in frequency or severity from expected levels are not to be considered adverse events. Examples of this may include, but are not limited to, teething, typical crying in infants and children and onset of menses or menopause occurring at a physiologically appropriate time.

Adverse events may occur during the course of the use of investigational product in clinical trials, or as prescribed in clinical practice, from overdose (whether accidental or intentional), from abuse and from withdrawal.

Progression of the cancer under study is not considered an adverse event.

All adverse events that occur after the consent form is signed, but before treatment allocation/randomization, must be reported by the Investigator if they cause the subject to be excluded from the trial, or are the result of a protocol-specified intervention, including, but

Product: MK-3475

Protocol/Amendment No.: Amendment 5, 21 October 2019

not limited to, washout or discontinuation of usual therapy, diet, placebo treatment or a procedure.

From the time of treatment allocation/randomization through 30 days following cessation of treatment, all adverse events must be reported by the Investigator. Such events will be recorded at each examination on the Adverse Event case report forms/worksheets. The reporting timeframe for adverse events meeting any serious criteria is described in section 9.1.3.1.

Adverse events will not be collected for subjects during the pre-screening period (for determination of archival tissue status) as long as that subject has not undergone any protocol-specified procedure or intervention. If the subject requires a blood draw, fresh tumor biopsy etc., the subject is first required to provide consent to the main study and AEs will be captured according to guidelines for standard AE reporting.

9.1.1 Definition of an Overdose for This Protocol and Reporting of Overdose to the Sponsor

For purposes of this trial, an overdose will be defined as any dose exceeding the prescribed dose for MK-3475 by 20% over the prescribed dose and an overdose of BCG is considered more than one vial of BCG administered per instillation, unless a greater number of vials are prescribed due to multi-focal disease.

In the event of an overdose, the event should be reported to the Sponsor and the subject should be observed closely for signs of toxicity. Appropriate supportive treatment should be provided, if clinically indicated. No specific information is available on the treatment of overdose of MK-3475. If over dosage of BCG occurs, the patient should be closely monitored for signs of active local or systemic BCG infection. For acute local or systemic reactions suggesting active infection, an infectious disease specialist experienced in BCG complications should be consulted.

If an adverse event(s) is associated with (“results from”) the overdose of a study drug, the adverse event(s) is reported as a serious adverse event, even if no other seriousness criteria are met.

If a dose of an investigational product meeting the protocol definition of overdose is taken without any associated clinical symptoms or abnormal laboratory results, the overdose is reported as a non-serious Event of Clinical Interest (ECI), using the terminology “accidental or intentional overdose without adverse effect.”

All reports of overdose with and without an adverse event must be reported within 24 hours to the Sponsor and within 2 working days to the manufacturer’s safety division (For Merck products this is Merck Global Safety, Attn: Worldwide Product Safety; [contact]).

